HV3 (between weeks 6-11)	
CHW inquires how patient and family are doing. Review care coordination, action plan, goals, medications, and relevant community resources.
 
Review use of tablet and PP:
 
 • Problems with use addressed • Complete at least 2 tasks with PP • Show how to email if not known already 	Email/phone to patient encouraging sign in to PP.
DC-week 12	Participant called by a member of the research team for data collection.	

Table 1 (continued). Activities and data collection (DC) for PT+HV and PT groups.

Time	PT+HV	PT
HV4 (between weeks 23-27)	CHW inquires how patient and family are doing. Review care coordination, action plan, goals, medications, and relevant community resources. Review use of tablet and PP: 
 • Problems with use addressed • Review how to “google”, email, and how to get weather and latest news on the internet 	Email/phone to patient encouraging sign in to PP.
DC – week 28	Participant meets with a data collector for data collection which includes spirometry.	
DC-week 36	Participant called by a member of the research team for data collection.	
DC week 48-50	Participant meets with a data collector for data collection which includes spirometry.	
DC every 12 weeks	Participant called by a member of the research team for data collection.	

CHW= community health worker, DC= data collection, PP= patient portal, PT= patient portal training, PT+HV= patient portal training plus home visits, HV1= first home visit, etc.

Patient Portal Training (PT)

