Educational attainment	X		
Health literacy –S-TOFHLA, ANQ, eHealth Literacy	X		
Comorbidities	X		
Depressive thoughts	X		
Primary language	X		

*Quarterly data collection occurs at months 3, 6, 9, and 12 and every 3 months after month 12 until the end of the study.

** We collect outcomes quarterly, at 12 months, and every 3 months until the study ends. Final visit is the final visit of data collection that occurs after the 12-month collection.

+Prednisone bursts are defined as a new prescription or an increase in dose of prednisone.

++FEV1 could be collected for only 203 patients owing to non-availability of spirometry equipment at the start of the study.

#The Inhaler Adherence Scale asks participant's report of non-adherence.^{29,30} It is a 6-item scale with each item scored 1 (non-adherence) or 0 (adherence). The range is 0-6, with 0 being optimal adherence.

Time frame for the study

All participants were to be followed for data collection every 3 months for at least 1 year (please see the Home Visitor Protocol sub-section and Figure 1). We chose a 3-month interval for data collection, as the Expert Panel Report uses 3 months for making a change such as “stepping down.”³¹ We chose the times for home visits, based on [name] experience with home visits in children. She found it was important to have home visits early in participation.³² We wanted the last 6 months to be for observation to assess sustainability. For reasons for withdrawals or becoming lost to follow-up, please see Figure 2.

Data collection and sources

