Irregular data collection times (see results) required models that used outcome time as a continuous measure. For that reason, analysis models implemented spline based marginal (GEE) (MCAR assumption) and mixed effects (MAR assumption) longitudinal models, both identity/Gaussian, log/Poisson, and log/gamma with marginal splines to estimate expected values of outcomes at 0 months and 12 months and outcome changes between 0 and 12 months. We used all data collection times and the actual times. We did not artificially categorize data collection times to equate to the preplanned 0, 12, 24, 36, and 48 weeks from randomization. The contrast (estimator) of interest was the difference between the treatment groups in the changes in expected values from 0 months to 12 months. Examples in the statistical literature support this approach.⁴⁵ All confidence bounds were estimated using 999 bootstrap resamples (percentile-based). By using 999 samples, confidence bounds are from the 25th and 975th order statistics without interpolation. Details appear in Appendix A7.

Model form

We used both marginal and mixed effects models, with the marginal model being the primary approach owing to convergence problems with mixed effect models (noted below).⁴⁶ By including splines for time and group-by-time interaction terms, these models could produce the expected values at 0 and 12 months and predicted values of interest.

For the primary outcome of asthma control, the skewed distribution of outcomes necessitated that we use log gamma models. The treating clinic was a stratifying factor in all models to account for the stratified randomization.

Alternative approaches for estimating asthma control

Differences between intervention groups in expected values at given follow up times, although statistically appropriate for comparing groups, lacks an immediate connection to the manner in which clinicians might want to interpret results. For that reason, we pre-planned two methods for translating findings into clinically useful metrics.

(1) Fraction of patients who have achieved asthma control (a level below 1.5 on the scale):

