study intervention. To that end, we modeled time using flexible splines. This approach is well-described in the statistical literature and implemented in standard statistical software packages. (4) With measures occurring over a continuous time line, and with final measures happening sometime before and some after the pre-planned 12-month goal, we compared the two randomized groups of patients as of the same, pre-planned 12-month time compared to baseline (date of randomization). We accomplished this task by estimating from our models the expected values or mean outcomes as of 0 months and 12 months. This task is routine with typical longitudinal data models, whether those models implement mixed effects or population averaged approaches. In either case, we estimated expected values at times 0 months and at 12 months. The contrast of interest in estimating the effects of the intervention versus control becomes a difference between groups of the within-group differences over time from 0 months to 12 months. This approach used all available data, distinguished, for example, between a final measurement at 11 months versus another at 14 months, and permitted standard methods of covariate adjustment for covariate imbalance arising out of the loss to follow up at any time during the study.

We consider our approach to be superior to some alternatives and especially to ad hoc approaches. First, we do not agree with conventional approaches that simply ignore discrepancies between pre-planned and actual interview times. If over time an intervention is effective in reducing asthma symptoms, then a patient should have a lower (better) asthma control score if he or she is interviewed at month 7 or 8 rather than at month 6. Second, we do not feel that treating time as categorical factor and adding a covariate that indicates whether the interview was inside or outside of a pre-specified window leads to unbiased estimates. There is little reason for this approach when time can be analyzed as a continuous measure. Third, approaches that use a patient's final measurement, even if it occurs before 12 months (pre-specified end date), as the final, 12-month measurement is simply another version of last observation carried forward (LOCF) approaches, which have been thoroughly discredited in numerous analyses, reports, and editorials. A final measurement at month 8 in theory will

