Appendix A7 (continued). Methods for handling Irregular data collection interviews - Unified modeling approach.

differ from the same patient's measurement at month 12. Fourth, although multiple imputation is a well-accepted option for missing outcomes when visit times are categorical, the approach is not practical when, as in our case, visit times can and do occur throughout the 12-month follow-up. Multiple imputation, as currently programmed, would necessitate that we impute all 12 months of data for each patient – a very large amount of missing observations to impute and thus a large fraction of monthly outcomes are missing by design. Finally, examples in the statistical literature support this suggested approach (Howe 2016).

Model form

The primary outcome is improvement in asthma control in both the intervention (PT + HV) and the control PT (Portal only) groups. The question of interest then is whether asthma control improved over time more in the PT + HV group compared to the control group, and did the control group improve over time. More formally, as the primary comparison of this primary outcome, the corresponding statistical estimand is the difference in expected values between the PT + HV group and the PT (control) group from baseline to 12 months after randomization date. To test the within group and across group effects of the interventions on outcomes we implemented mixed effects models (using restricted maximum likelihood and adaptive quadrature) and marginal models (using generalized estimating equations (GEE)) as a unified approach for the analysis of the longitudinal data with baseline randomization. For within-group outcomes, these models use all available data to estimate changes over time. Both the mixed effects and marginal models can be used for continuous, binary, and count outcomes using linear, logistic, and log linear models that can compare changes over time in the outcomes of asthma control, quality of life, ED visits, hospitalizations over one year. (Fitzmaurice, Laird, Ware 2011). By including group-by-time interaction terms, these models can then be adapted to compare improvement over time between the patient portal plus home visit group and the portal only group.

Each type of model has its strengths and weaknesses. While the GEE method benefits from simplicity and robustness, it requires stronger assumptions about dropout (dropout

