departure of the individual over time from the average trajectory not explained by these observed covariates. The model converged. We then added a second random slope to represent an additional element of individual patient departure from average as the follow-up time progressed. This model converged in 10 iterations. Models with additional random slopes to reflect the additional time segments of the spline model would not converge.

The final model, included as fixed effects: Linear (marginal) spline with knots at 3,6, 9, and 12 months; clinic, Spanish as the primary language, age categorized (18-39, 40-49, and 50+), literacy levels (4 levels from latent class models), social support(3 levels from latent class models), smoking exposure(4 –levels: none, first hand smoke only, second hand smoke only, both first and second hand smoke), comorbidities (3-level latent class model: healthy, depressed, other chronic comorbidities), baseline asthma severity (low high), concern about using health data on the internet (5 levels), home crowding (3 levels: <1 per room, 1 up to 2 per room, 2+ per room).

Random effects included: a random intercept for subject and a random slope for the first two line segments constructed by the spline model.

This analysis can best be thought of as a sensitivity analysis to the main findings of the asthma control outcome. Its limitations are that there were insufficient data to fit a log-link, gamma-family model with more than 2 random slopes.

References

2. Morris CN. Parametric empirical Bayes inference: Theory and applications. J. Amer. Statist. Assoc. 1983;78:47–65. with discussion.
3. Casella G. An introduction to empirical Bayes data analysis. Amer. Statist. 1985;39:83–87.

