Additional assumptions implied by this approach are (4) random assignment and (5) that at least some patients complied with the protocol and met with the home visitors having been randomized to that arm. Both implied assumptions were satisfied in our study.

Based on the assumptions, we determined that the instrumental variable approach might help to estimate the effect of home visits among those who complied with the home visit protocol.

Measuring adherence

To implement the instrumental variable approach, we measured adherence as follows. The data collection times at the protocol were 0 12 24 36 and 48 weeks. The scheduled home visit times were baseline, 3, 5, 8, and 25 week. But many patients could not or did not follow either plan. For reasons of difficulty in scheduling both the home visit and the data collection, patients' actual schedules slipped, sometimes by more than a few months, from the schedule specified by the protocol.

By comparing the dates of the actual home visits with the dates of the actual outcome data collection, we could determine for each data collection the number of home visits that the patient should have completed as of the data collection date and compare that number to the number of home visits actually received at that time. For example, if the patient had a first post-baseline data collection as of day 90 and by that time the patient should have received three home visits, the expected number of visits = 3. If the patient had received only 2 home visits as of that time, then the ratio of actual to expected number of visits = $2/3 = 0.67$. We then concluded that falling behind in the home visit schedule could attenuate the effect of the home visitor, and for that reason, we categorized each patient at each visit as adherent if this ratio was greater than or equal to 1.0 and non-adherent otherwise.

Estimating the effect of home visits under complete adherence

Appendix A10 (continued). Estimating effect of home visitors adjusted for incomplete adherence – A sensitivity analysis.

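### For ED visits and hospitalizations the only between-arm contrast described compares month 12 with month 0; if counts run from the last interview, events during the home-visit period do not enter it, and no event rate over follow-up is planned

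*Combined protocol and SAP*

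**What the plan says.** The main text (Modeling approach – flexible modeling of time) describes marginal and mixed models in several families, including "log/Poisson, and log/gamma with marginal splines to estimate expected values of outcomes at 0 months and 12 months", and then gives one estimator: "The contrast (estimator) of interest was the difference between the treatment groups in the changes in expected values from 0 months to 12 months". Appendix A7, under its methods for irregular collection times, repeats it as a "difference between groups of the within-group differences over time from 0 months to 12 months".

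Appendix A7, Model form, says these models can "compare changes over time in the outcomes of asthma control, quality of life, ED visits, hospitalizations over one year". Prednisone bursts are an outcome in Table 2 but are not in that list.

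On timing, the Table 2 footnote says: "Quarterly data collection occurs at months 3, 6, 9, and 12". Events are self-reported (Study Outcomes), with no recall period given. Table 1 schedules the first home visit at weeks 2-4 and the fourth at weeks 23-27. The section on the study's time frame keeps the last six months for observing whether effects last. Appendix A10 reports that patients' "actual schedules slipped, sometimes by more than a few months", for home visits and data collection alike.

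The two clinically framed metrics and the endpoint fixed for the sensitivity analyses concern asthma control only. The Trial monitoring section describes an external board that reviewed data every six months and monitored unexpected ED visits and hospitalizations.

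**The concern.** A change between two time points suits the asthma control score, which reflects the past week. ED visits and hospitalizations accrue over time. If an interview records events since the previous one, the month-0 value describes time before randomization and the month-12 value describes roughly the last quarter. The home visits are scheduled between those two intervals, so the contrast would set pre-trial events against observation-phase events and leave out the delivery period. The same holds for prednisone bursts if they are fitted with the same models.

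These outcomes matter to patients, and unexpected ED visits and hospitalizations are the serious adverse events the safety board monitored. A transient benefit or excess could be reported as no difference, and a lasting one would be estimated far less precisely than the collected data allow. No exposure time is described either, although slipped interviews would make since-last-interview windows unequal.

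**Working it through.** **The plan's own power figure.** It concerns asthma control only: 300 evaluable patients, a difference of 1/3 SD, power 0.82 to 0.87. With 150 per arm and two-sided 0.05 (assumed from the 95% percentile bounds), z = (1/3) × √(150/2) = 2.887, and Φ(2.887 − 1.960) = 0.823. The lower end reproduces. The upper end depends on within-patient correlations that are not given. No event rate or power is stated for ED visits or hospitalizations, so the event rates and effects below are assumptions.

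**What the contrast estimates.** Write Y_a(t) for the expected count reported at month t in arm a. The contrast is [Y₁(12) − Y₀(12)] − [Y₁(0) − Y₀(0)]. Randomization makes the second bracket zero in expectation, so only the month-12 difference remains.
- *Counts since the last interview:* the month-12 count covers about months 9-12. An effect confined to weeks 2-27 does not reach it, so the expected contrast is about 0.
- *Same counts, rate halved through month 12 at 1 event per year:* −0.5 × 1 × 0.25 = −0.125 per quarter.
- *Past-12-month counts at both ends:* the contrast equals the full-year difference, and the home-visit period is included.

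**Size of a transient effect.** At 1 event per patient-year, weeks 2-27 hold 25/52.18 = 0.479 events. Halving the rate removes about 0.24 per patient (about 36 per 150); doubling adds about 0.48 (about 72 per 150).

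**Simulation, counts since the last interview.** Poisson counts with gamma frailty (variance 1); interviews at months 0, 3, 6, 9 and 12 with random delays; arm-by-linear-spline log/Poisson model with independence working correlation and a log time-at-risk offset. Knots are at 3, 6, 9 and 12 months, which Appendix A8 gives for asthma control ("Linear (marginal) spline with knots at 3,6, 9, and 12 months"); using them for counts is an assumption. Expected values come from 60,000 per arm. Rejection rates come from 300 trials of 150 per arm, with robust Wald intervals in place of the bootstrap.

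| Events/year | Effect | Difference in events per 150 | Contrast per quarter (SE) | Contrast significant | Rate ratio | Rate ratio significant |
|---|---|---|---|---|---|---|
| 0.5 | halved, weeks 2-27 | −17.9 | 0.000 (0.004) | 4% | 0.77 | 24% |
| 0.5 | doubled, weeks 2-27 | +35.9 | −0.003 (0.003) | 3% | 1.45 | 49% |
| 1 | halved, weeks 2-27 | −35.9 | −0.004 (0.005) | 6% | 0.77 | 34% |
| 1 | doubled, weeks 2-27 | +71.8 | −0.001 (0.005) | 6% | 1.45 | 72% |
| 2 | halved, weeks 2-27 | −71.8 | +0.002 (0.007) | 3% | 0.78 | 42% |
| 2 | doubled, weeks 2-27 | +143.5 | +0.005 (0.007) | 4% | 1.46 | 82% |
| 1 | halved from week 2 on | −72.1 | −0.128 (0.005) | 22% | 0.52 | 95% |

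The last row agrees with the −0.125 derived above. With 300 trials, the Monte Carlo SE at 5% is √(0.05 × 0.95/300) = 0.013, so 3-6% is the nominal error rate. The model already carried an offset, so an offset alone does not repair the contrast.

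The same fit does show the effect between the endpoints. At 1 event per year, the arm differences at months 3 and 6 are −0.105 and −0.130 per quarter for halving, and +0.203 and +0.275 for doubling.

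**Sustained 40% excess, 1 event per patient-year, 150 per arm.** In a second simulation (400 runs, mean interview delay 1 month), the SD under no effect is 0.383 for the log contrast and 0.166 for the log rate ratio, a variance ratio of (0.383/0.166)² = 5.3. Power was 0.145 against 0.63. A normal approximation with log 1.4 = 0.336 gives 0.336/0.383 = 0.88, hence power 0.14. For the rate ratio, an SD of 0.166 gives 0.53 and an SD of 0.15 (the low end seen) gives 0.61. A third simulation gave about 0.13 against 0.48. It also gave 67% for the rate ratio when the rate doubles during home visits only, with the contrast significant in about 4-6%.

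**The case against.** The strongest objection is that the recall period is assumed. The only period the documents attach to such events is the past-year eligibility criterion. If the interviews used the same window, the contrast would cover the whole year, and the closing phrase of the Appendix A7 list can be read as annual counts. This stands, and it makes the point conditional. But past-year recall repeated every quarter would count one event up to four times, and the inhaler adherence items ask about three months. If annual totals were meant, the stated estimator does not say so.

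A reader might go further and infer that events in the home-visit period drop out and cannot be seen. The documents do not support that. Every interview is used in the fit, the curves can be read at months 3 and 6, adverse event forms were scheduled at weeks 12, 24, 36 and 48 (Appendix A1), and the external board monitored these events. What remains is narrower: none of these is a planned between-arm estimate.

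The zero contrast also follows from assuming an effect that stops with the visits. An effect lasting to month 12 would show, at low power. Home visits slipped too, so some delivery may have fallen later than weeks 23-27. Lastly, month 12 is the pre-planned comparison time and answers the sustainability question. That is a reason to keep the contrast, but not to have nothing beside it.

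**Conclusion.** The point holds conditionally. As written, the month-0-to-12 change is the only between-arm contrast described for ED visits and hospitalizations, and for prednisone bursts if they are modeled the same way. Given counts since the last interview, an effect confined to the home-visit period averages to about zero at every assumed rate from 0.5 to 2 events per year. A sustained 40% excess at 1 event per year has power of about 0.13-0.15, against 0.48-0.63 for a rate ratio over follow-up. Under past-12-month recall at both ends the loss disappears, so the unstated recall period is part of the defect. The figures rest on the assumed event rates, frailty, delays and knots. The primary outcome and its power statement are unaffected. The change should be made, because these are patient-important secondary outcomes and the data are already collected.

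**What to change.** 1. State the recall period of each event question at enrollment and at follow-up.
2. Reconcile the one-year wording in Appendix A7, Model form, with the month-0-to-12 contrast in the main text.
3. Add, for ED visits, hospitalizations and prednisone bursts, a between-arm rate ratio over follow-up from randomization: log/Poisson, offset equal to the log of the person-time covered by completed interviews, clinic strata, baseline count as covariate, and the existing 999-resample percentile bootstrap at patient level. Use the full interval of an interview that spans month 12. If recall proves to be the past 12 months, overlapping quarterly counts must not be summed.
4. Keep the month-0-to-12 contrast for asthma control and quality of life, and as the sustainability comparison for events.

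The cost is some added text and a simple model on data in hand, once the interval behind each count is defined. The downside is a second estimand for secondary outcomes. The document describes its analyses in the past tense, so the rate ratio should be labeled supplementary if outcomes have already been seen.
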